4.2 PHARMACODYNAMICS

4.2.1 *Available data*

The following PD parameters will be measured:

- ██████████
- Anti-BP180 antibodies and anti-BP230 antibodies

4.2.2 *Derivation rules*

BQL or AQL values will be handled as described in section 2.3.3.

Samples for anti-BP180 antibodies and anti-BP230 antibodies will be diluted until the result falls within the reportable range of [20-200 RU/mL]. For anti-BP180 antibodies:

	Statistical Analysis Plan	
ARGX-113-2010	Final analysis	Final 1.0 of 29APR2025

- The value for analysis will be the result with the lowest dilution factor and with value ≤ 200 RU/mL, multiplied by the dilution factor.
- If the result is < 20 RU/mL, the value for analysis will be imputed by 20 RU/mL, multiplied by the dilution factor.
- If at a dilution factor (D1) the result is above 200 RU/mL, and at the next higher dilution factor (D2) the result is < 20 RU/mL, the value for analysis will be derived as $D1 \times 200$ RU/mL.
- If all the results up to dilution factor 32 are above 200 RU/mL, then the value for analysis will be imputed by 6400 RU/mL (32×200), even if the result at a higher dilution factor gives a value below 6400 RU/mL.
- If the result is above 200 RU/mL in the original non-diluted sample and no higher dilution factors are available, the value for analysis will be imputed by 200 RU/mL.
- Multiplication by the dilution factor will be done at analysis level if not yet done by the lab.

For anti-BP230 antibodies:

- If in the original (non-diluted) sample the result is above 200 RU/mL, then the value for analysis will be imputed by 200 RU/mL, even if the result at a higher dilution factor is ≤ 200 RU/mL.
- If the result in the original sample is < 20 RU/mL, the value for analysis will be imputed by 20 RU/mL.

Changes and percent changes versus TPnB will be calculated. Treatment periods with a TPnB value below the limit of quantification (BLQ) or with a result < 20 RU/mL (for anti-BP180 and anti-BP230 antibodies) will be excluded when presenting the actual values, the changes from TPnB and the percent changes from TPnB. This will be explained by a footnote in the appropriate tables.

In addition, for all pharmacodynamic endpoints, descriptive statistics of the actual values and percent changes from baseline will also include GM and GSD. GM and GSD of percent changes from baseline are calculated as $100X \{ \exp(\theta) - 1 \}$ where θ is respectively the arithmetic mean and arithmetic SD of a variable calculated as $\log(\text{aval}) - \log(\text{base})$. GM and GSD are not applicable for descriptive statistics of the absolute changes from baseline.

4.2.3 *Presentation of results*

The SAF analysis set will be used for the PD evaluation. For tables by analysis visit, only the TPnB and last assessment analysis visits in a treatment period will be shown. Results for treatment period 2 will only be presented if at least 10 participants have a post-TP2B PD assessment.

All pharmacodynamic endpoints will be summarized by means of descriptive statistics at each analysis visit of interest in a treatment period. Actual values, changes from TPnB and percent changes from TPnB will be tabulated. Descriptive statistics of the actual values and percent changes from TPnB will also include GM and GSD. GM and GSD are not applicable for descriptive statistics of the absolute changes from TPnB.

	Statistical Analysis Plan	
ARGX-113-2010	Final analysis	Final 1.0 of 29APR2025

Listings will be created for [REDACTED] and anti-BP antibodies results over time, based on the ROL analysis set. Listings will always show the non-imputed results.

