3. OBJECTIVES, ENDPOINTS, AND ESTIMANDS

Table 4: Study ARGX-113-2010 Objectives and Endpoints

Objectives	Endpoints
Primary	
To assess the long-term safety and tolerability of treatment with efgartigimod PH20 SC in participants with BP	
 • Incidence and severity of treatment-emergent AEs, SAEs, and AESIs • Rate of treatment discontinuation because of safety concerns
Secondary	
To assess the long-term efficacy and durability of response with efgartigimod PH20 SC treatment in participants with BP	
 • Proportions of participants achieving^a: 
 – CR while off OCS for ≥ 8 weeks – CR or PR while off OCS for ≥ 8 weeks – CR while on minimal OCS therapy for ≥ 8 weeks. (Minimal OCS therapy is defined as ≤ 0.10 mg/kg/day of prednisone [or an equivalent dose of another OCS]) – CR while off both OCS and efgartigimod PH20 SC for ≥ 8 weeks^b – CR or PR while off both OCS and efgartigimod PH20 SC for ≥ 8 weeks^b • Duration of sustained remission • Proportion of participants who relapse • Time to relapse • Incidence and severity of relapse • BPDAI activity scores, IGA-BP scores, and itch NRS over time • Rate of treatment failure
Additional secondary	
To evaluate the impact of efgartigimod PH20 SC treatment in reducing long-term glucocorticoid-associated toxicity in participants with BP	GTI-related scores, including the GTI-AIS, GTI-CWS, and GTI-SL over time
To evaluate the impact of efgartigimod PH20 SC treatment on QoL in participants with BP	EQ-5D-5L, DLQI, and ABQoL scores over time
To evaluate the PD and immunogenicity of efgartigimod PH20 SC in participants with BP	
 • Percent change from baseline over time for anti-BP180 and anti-BP230 antibody levels • Incidence and prevalence of ADA against efgartigimod (serum levels)

Objectives	Endpoints
Exploratory	
████████████████████ ████████████████████	██ ████████

^a These endpoint criteria can only be met when participants are off rescue therapy.

^b The endpoint applies only to participants who have stopped receiving efgartigimod PH20 SC before protocol amendment 2 is effective.

No estimands have been defined for this OLE study.

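### Anti-BP180 samples above 200 RU/mL are analysed as 200 if no dilution was run but at up to 6400 if it was, so a mismatch between the two tabulated visits produces a spurious percent change

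*SAP*

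**What the plan says.** The endpoint, listed as additional secondary in Protocol section 3 (Table 4) and SAP Table 1, is "Percent change from baseline over time for anti-BP180 and anti-BP230 antibody levels". SAP 4.2.2 and 4.2.3 compute and tabulate it against TPnB.

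SAP 4.2.2 intends that samples "will be diluted until the result falls within the reportable range of [20-200 RU/mL". For anti-BP180 it then sets these rules:

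- **Normal case:** "The value for analysis will be the result with the lowest dilution factor" that reads no more than 200, multiplied by that factor.
- **Top of the diluted range:** "If all the results up to dilution factor 32 are above 200 RU/mL, then the value for analysis will be imputed by 6400 RU/mL".
- **Fallback:** "If the result is above 200 RU/mL in the original non-diluted sample and no higher dilution factors are available", the analysis value is set to 200.

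Anti-BP230 is handled differently. Any undiluted result above 200 is set to 200, "even if the result at a higher dilution factor is ≤ 200 RU/mL". Every anti-BP230 sample therefore shares one ceiling.

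At the low end, SAP 4.2.2 drops a treatment period from the actual values, changes and percent changes when TPnB is below quantification or under 20 RU/mL, with a footnote. No counterpart exists for a TPnB known only to exceed 200. SAP 4.2.3 tabulates only TPnB and last assessment in each treatment period, with geometric mean (GM) and geometric SD added to the usual statistics. Listings show the non-imputed results.

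**The concern.** A result above 200 with no dilution is right-censored: its true value may lie anywhere above 200. The fallback enters it as the lowest value it could have and treats it as measured. That alone is ordinary limit substitution. The difficulty is that the same participant's other visit may have been diluted and so be measured on a range reaching 6400. The percent change then divides a value under one ceiling by a value under another, and the ceiling is chosen by whether a dilution was run, not by the antibody level.

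Because only two visits are tabulated, one such sample fixes that participant's whole contribution to the table. The SAP gives no flag, exclusion or sensitivity analysis for these values, and section 2.3.5 rules out any outlier step. At stake is the summary of how far the drug lowers a pathogenic autoantibody.

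**Working it through.** **The plan's own figure.** 32 × 200 = 6400 RU/mL. This reproduces the stated upper imputation value.

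**Inputs from SAP 4.2.2 and 2.2.2.** Reportable range 20 to 200 RU/mL; ceiling 6400 with dilution and 200 without. Percent change = 100 × (value − TPnB) / TPnB. GM percent change = 100 × (exp(θ) − 1), with θ the mean of log(value) − log(TPnB). Assumed: an error-free assay.

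**One participant, true level unchanged.**

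| True level | Baseline undiluted, last diluted | Baseline diluted, last undiluted |
|---|---|---|
| 250 | +25% | -20% |
| 400 | +100% | -50% |
| 800 | +300% | -75% |
| 1600 | +700% | -87.5% |
| 6400 | +3100% | -96.9% |

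For 1600: 100 × (1600 − 200)/200 = +700%, and 100 × (200 − 1600)/1600 = -87.5%.

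**One participant, true 75% fall from 1600 to 400.** Both diluted: -75%. Only the last undiluted: 200 against 1600, -87.5%. Only the baseline undiluted: 400 against 200, +100%. Neither diluted: 200 against 200, 0%.

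**Group effect, simplest case.** Assume a share s of participants sit at an unchanged 1600 with an undiluted baseline, and all others have 0% change. The arithmetic mean is s × 700% and the GM change is 100 × (exp(s × ln 8) − 1). At s = 0.10 these are +70% and +23.1%. With the last sample undiluted instead, they are -8.8% and -18.8%.

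**Group effect, simulated.** Assumptions, none from the documents: 400,000 pairs; lognormal baseline, median 1000, log-SD 1; every true level falls by 40%; values limited to 20–6400; dilution lost at random among values above 200. With no loss the GM change is -39%, not -40%, because the limits trim the extremes.

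| Loss of dilution | Last sample only (GM) | Baseline only (GM) | Both visits (GM) |
|---|---|---|---|
| 2% | -41% | -37% | -39% |
| 5% | -43% | -34% | -38% |
| 10% | -46% | -29% | -37% |

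The arithmetic mean is more exposed to baseline cases. At 10% loss it moves from -39% to about +2% (baseline only) or about -5% (both visits). The median stays at -40%, but only because every simulated participant falls by the same 40%; the run does not test the median's robustness.

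**The case against.** The case for leaving the rule alone has real weight.

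- **It is a fallback.** Dilution is the planned procedure, and the documents do not say how often, or whether, a sample above 200 went undiluted. At 2% loss the GM moves by about two points or less.
- **Limit substitution is the SAP's convention.** The 6400 ceiling is itself a right-censored value treated as measured.
- **The stakes are low.** The endpoint is additional secondary, there is no hypothesis testing, the median and quartiles are tabulated, and the listings let each case be traced.
- **Exclusion has its own bias.** It removes only values above 200 and discards some knowledge: baseline 100 with a last value above 200 is at least a doubling.

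All of this limits the size of the point, and the last item shapes the fix. None of it repairs the tables. The convention argument does not reach the specific fault, which is two ceilings within one ratio; the anti-BP230 rule avoids that, and the low-end baseline rule shows that the SAP already accepts exclusion with a footnote.

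A reader might go further and infer that an undiluted last sample always shows a large fall, and an undiluted baseline always a large rise. The rules do not give that. With an undiluted last sample, a baseline of 250 reads -20% and a baseline of 100 reads +100%. With an undiluted baseline, a true change from 1600 to 100 reads -50%, an understated fall. A reader might also infer that the rule favours the drug. The direction depends on which visit lacks dilution, and equal loss at both visits pulls the simulated GM slightly towards no effect.

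**Conclusion.** The point holds in a conditional form. When only one of TPnB and last assessment lacks dilution, and the diluted value is well above 200, the tabulated anti-BP180 change is an artefact of dilution history: -87.5% or +700% for an unchanged 1600. When both lack dilution, a change that stays above 200 is reported as 0%. This follows from SAP 4.2.2 as written and needs no assumption about frequency.

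The effect on the group summary does rest on assumptions. With 2% to 10% loss in the assumed population, the GM change ranges from -29% to -46% against -39% with no loss, and baseline-only loss at 10% removes the apparent fall in the arithmetic mean. The documents do not show that the table will be materially wrong, because they do not give the number of affected samples. No primary safety result, test or sample size is touched. It should be corrected because the rule anticipates such samples, the tables are unprotected, and the change is small.

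**What to change.** Replace the fallback bullet in SAP 4.2.2 with wording to this effect:

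*An anti-BP180 result above 200 RU/mL with no dilution result available is treated as right-censored (>200). It is reported as >200 and is not evaluable for change or percent change from TPnB. It keeps its place as TPnB or last assessment; no earlier sample is substituted. The number of such samples at TPnB and at last assessment is footnoted. A sensitivity summary repeats the table with these values set to 200, or with a common cap of 200 at both visits.*

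The no-substitution sentence is needed because SAP 2.2.2 and 2.2.6 select the last non-missing value, so an unqualified exclusion could bring in an older sample. The common cap restores one scale but hides falls that stay above 200 (1600 to 400 reads 0%), so it suits a sensitivity analysis only.

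**Cost.** One bullet, one footnote and one extra summary. The number of evaluable pairs drops slightly: with independent loss, at most 1 − 0.98² = 4.0% of pairs at 2% loss per visit and 1 − 0.90² = 19% at 10%. The main downside is selective loss of high values if missing dilution is related to level; the footnote count and sensitivity summary disclose it. Rerunning stored samples at dilution is optional. Protocol 8.1.1 provides for storage, but the documents do not show whether a rerun is feasible.

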1.1 STUDY OBJECTIVES AND ENDPOINTS

Table 1: Objectives and endpoints

Objectives	Endpoints
Primary	
To assess the long-term safety and tolerability of treatment with efgartigimod PH20 SC in participants with BP	
 • Incidence and severity of treatment-emergent AEs, SAEs, and AESIs • Rate of treatment discontinuation because of safety concerns
Secondary	
To assess the long-term efficacy and durability of response with efgartigimod PH20 SC treatment in participants with BP	
 • Proportions of participants achieving^a: 
 ○ CR while off OCS for ≥ 8 weeks ○ CR or PR while off OCS for ≥ 8 weeks ○ CR while on minimal OCS therapy for ≥ 8 weeks. (Minimal OCS therapy is defined as ≤ 0.10 mg/kg/day of prednisone [or an equivalent dose of another OCS]) ○ CR while off both OCS and efgartigimod PH20 SC for ≥ 8 weeks^b ○ CR or PR while off both OCS and efgartigimod PH20 SC for ≥ 8 weeks^b • Duration of sustained remission • Proportion of participants who relapse • Time to relapse • Incidence and severity of relapse • BPDAI activity scores, IGA-BP scores, and itch NRS over time • Rate of treatment failure

	Statistical Analysis Plan	
ARGX-113-2010	Final analysis	Final 1.0 of 29APR2025

Additional secondary	
To evaluate the impact of efgartigimod PH20 SC treatment in reducing long-term glucocorticoid-associated toxicity in participants with BP	
 GTI-related scores, including the GTI-AIS, GTI-CWS, and GTI-SL over time
To evaluate the impact of efgartigimod PH20 SC treatment on QoL in participants with BP	
 EQ-5D-5L, DLQI, and ABQOL scores over time
To evaluate the PD and immunogenicity of efgartigimod PH20 SC in participants with BP	
 Percent change from baseline over time for anti-BP180 and anti-BP230 antibody levels Incidence and prevalence of ADA against efgartigimod (serum levels)
Exploratory	
[REDACTED]	
 [REDACTED]

- ^a These endpoint criteria can only be met when participants are off rescue therapy.
- ^b The endpoint applies only to participants who have stopped receiving efgartigimod PH20 SC before protocol amendment 2 is effective.

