1.3 STATISTICAL HYPOTHESIS

No formal hypothesis testing will be conducted in this open-label study.

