Adverse events will be allocated to phases as described in section 5.1.2. Concomitant therapies and procedures will be allocated to phases and (sub)periods as described in section 3.3.2. All other assessments will be allocated to phases and (sub)periods based on the assessment date/time. In case of (partially) missing date/time fields disabling allocation of an assessment to phases or (sub)periods, information from the visit label, time point label and the protocol schedule of activities will be used to allocate to the correct phase.

For efficacy assessments without time part, an assessment on the day of switch from observation phase to treatment phase will be considered as part of the treatment phase. Likewise, an assessment on the day of switch from treatment period 1 to treatment period 2 will be considered as part of treatment period 2.

2.2.2 *Baseline and change from baseline*

Study baseline is defined as the first available and nonmissing value at the baseline visit (scheduled or unscheduled) in ARGX-113-2010. This value corresponds with the value at the EoTP visit in ARGX-113-2009 (and is copied over into the database of ARGX-113-2010 at SDTM level).

Change from baseline is defined as:

- Change from baseline at time point t = value at time point t – baseline value.

Percentage change from baseline at time point t is defined as follows:

- When baseline value is not zero: $100 * ((\text{value at time point } t - \text{baseline value}) / \text{baseline value})$
- When both baseline value and value at time point t are zero: 0
- When baseline value is zero and value at time point t is not zero: not calculated

For immunogenicity assessments, the study baseline selection will be performed by sample (not by parameter) in order to keep the ADA and NAb results of a sample together. Furthermore, values resulting in an unevaluable ADA status are given the lowest priority when the selection is made.

For evaluation of PD parameters, a treatment period-specific baseline (TPnB) will be defined:

	Statistical Analysis Plan	
ARGX-113-2010	Final analysis	Final 1.0 of 29APR2025

- For a treatment period, TPnB is the last available and non-missing value prior to the first IMP administration in the treatment period. Assessments on day 1 of a treatment period without time collection or with time information exactly equal to the time of first IMP administration and which are planned predose will be considered as predose.

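### The anti-BP antibody table drops every treatment period that starts below 20 RU/mL, even from the actual-value columns, so it shows falls across the cut-off but never rises

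*SAP*

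**What the plan says.** The endpoint is additional secondary: "Percent change from baseline over time for anti-BP180 and anti-BP230 antibody levels" (SAP 1.1). SAP 4.2.2 has three parts that matter here.

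- **Floor.** For anti-BP230: "If the result in the original sample is < 20 RU/mL, the value for analysis will be imputed by 20 RU/mL". For anti-BP180 the same floor applies, multiplied by the dilution factor.
- **Exclusion trigger.** "Treatment periods with a TPnB value below the limit of quantification (BLQ) or with a result < 20 RU/mL".
- **Scope.** Such periods "will be excluded when presenting the actual values, the changes from TPnB and the percent changes from TPnB". On disclosure: "This will be explained by a footnote in the appropriate tables". No count of excluded periods is specified.

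SAP 2.2.2 defines the baseline: "TPnB is the last available and non-missing value prior to the first IMP administration in the treatment period". SAP 4.2.3 restricts the PD tables to TPnB and the last assessment in a period, and SAP 2.2.6 lets follow-up samples serve as that last assessment. Table 14.2.3.2 is the only planned anti-BP table. Listing 16.2.6.13 gives non-imputed results over time for the rollover set.

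**The concern.** The SAP gives a result below 20 RU/mL a usable analysis value, then discards it when it falls at baseline, together with every later value in that period, including fully quantifiable ones. The same result is kept when it falls at the last assessment. Whether a participant appears in the table therefore depends on the direction of movement across the cut-off.

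This has more force in an extension study than in a first-exposure trial. The first period's TPnB is taken at or after rollover, which requires the week 36 visit of ARGX-113-2009. The former efgartigimod arm continues weekly dosing, and the drug is expected to lower autoantibodies (protocol 2.1). A low TPnB may come from that treatment, or from OCS or rescue therapy, and such a participant could only show a stable low level or a rise. The rule removes both patterns from the summary. No test is at risk ("No formal hypothesis testing will be conducted in this open-label study"), but in a descriptive study the summary tables are the result, so the periods they cover matter.

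**Working it through.** The plan states no figure for this rule, so there is none to reproduce. The check has three steps.

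**1. The rule applied to each type of period**

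| TPnB | Last value | Actual values | Change and percent change |
|---|---|---|---|
| 20 or more | 20 or more | shown | shown |
| 20 or more | below 20 | shown, last value = 20 | shown |
| below 20 | 20 or more | dropped | dropped |
| below 20 | below 20 | dropped | dropped |

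The third row has no counterpart in any other table. SAP 2.1.2 pools the former arms, and the SAP defines no PD summary against the ARGX-113-2009 baseline, although protocol 9.3.1 would allow one. The tables therefore cannot separate participants suppressed earlier from those who never had that antibody above the cut-off.

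**2. Made-up example of ten periods (illustration only)**

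TPnB: 10, 12, 15, 18, 40, 60, 80, 100, 150, 200. Last value: 60, 12, 90, 15, 30, 40, 50, 60, 80, 100. Values below 20 are set to 20. Geometric-mean change = 100 × (exp(mean log ratio) − 1), as in SAP 4.2.2.

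- SAP rule, n = 6: mean last value 60.0; mean change −45.0. The product of ratios is 0.75 × 0.667 × 0.625 × 0.6 × 0.533 × 0.5 = 0.05, and 0.05^(1/6) = 0.607, a change of −39.3%. Rises shown: 0.
- All periods, n = 10: mean last value 55.0; mean change −16.0. The four restored ratios are 3, 1, 4.5 and 1, so the product is 0.05 × 13.5 = 0.675, and 0.675^(1/10) = 0.961, a change of −3.9%. Rises shown: 2.

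**3. Size when nothing truly changes**

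The documents give no antibody distribution, so every input is an assumption: log-normal levels, between-participant log SD 1.0, within-participant log SD w of 0.3 to 0.5, geometric mean (GM) 15, 30 or 60 RU/mL, floor 20, and 400,000 simulated periods per scenario. The expected share excluded is Φ[(ln 20 − ln GM)/√(1 + w²)]. For GM 30 and w = 0.3 this is Φ(−0.405/1.044) = Φ(−0.388) = 35%, as simulated. Ranges below run from w = 0.3 to w = 0.5.

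| GM | Excluded | Excluded periods ending at 20 or more | Last-value GM, retained | Last-value GM, all periods | GM change, retained | GM change, all periods |
|---|---|---|---|---|---|---|
| 15 | 60–61% | 10–17% | 40 | 27–28 | −4% to −10% | about 0 |
| 30 | 35–36% | 17–27% | 53–54 | 38–40 | −2.6% to −6.7% | about 0 |
| 60 | 15–16% | 26–39% | 78–80 | 65–66 | −1% to −4% | about 0 |

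At GM 30, rises across the cut-off make up 0.348 × 0.173 = 6.0% (w = 0.3) to 0.358 × 0.267 = 9.6% (w = 0.5) of all periods. By symmetry falls are equally frequent. The table shows all the falls and none of the rises.

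A second set of assumptions has half the participants previously on efgartigimod, untreated GM 30 to 120, between-participant log SD 1.2 and prior suppression of 40% to 80%. It gives 11% to 60% excluded overall (15% to 83% of prior-efgartigimod periods, 7% to 38% of the others) and a false fall of 0.7% to 7.1%.

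**The case against.** The endpoint is percent change, and a baseline at the floor cannot show a fall, so excluding it there is reasonable. Using one set of periods for all three columns lets baseline, last value and change reconcile. Restoring the excluded periods fills the actual-value columns with placeholder 20s: at GM 30 the all-periods figure is 38 to 40, not 30.

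The first argument stands, and the fix respects it. The second is a fair presentational reason, but showing a separate n for each column meets it. The third is only partly right. The SAP already accepts placeholders at the last assessment: at GM 30 about 9% (0.060/0.652) to 15% (0.096/0.642) of retained last values sit at the floor. A last-value GM of 53 to 54 is also further from 30 than 38 to 40 is.

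Four stronger readings are tempting, and the documents do not support them.

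- *The data are lost.* They are not. The listing keeps them unimputed and the table will carry a footnote. The exclusion is also by treatment period and, on the natural reading, by antibody, so a participant can still contribute elsewhere.
- *Participants are removed because they responded well.* This is possible but not shown. A value below 20 may equally mean that the antibody was never above the cut-off, and no seropositivity rate is given.
- *The table would otherwise show loss of suppression on weekly dosing.* Not as it stands, because the last assessment can be a follow-up sample taken off drug.
- *Restoring the actual values corrects the false fall.* It does not. That fall belongs to the change statistics and remains while the baseline exclusion applies to them.

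**Conclusion.** The point holds for the summary table. Extending the exclusion to actual values is unnecessary, because "the value for analysis will be imputed by 20 RU/mL" already supplies a value, and it makes Table 14.2.3.2 one-sided around 20 RU/mL. No other table recovers the excluded periods.

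The size cannot be fixed from the documents. Under the stated log-normal assumptions roughly 15% to 61% of periods would be excluded, and the false fall in the retained periods is modest, about 1% to 10%. The larger effects are the raised actual-value summaries and the uncounted rises. The issue concerns one additional secondary PD endpoint and no hypothesis test. It is worth correcting because the correction is cheap, not because it threatens the study's main conclusions.

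**What to change.** 1. **Actual values.** Summarise them, floored at 20 RU/mL, at TPnB and post-TPnB for all safety-set treatment periods with a sample, with a footnote on the floor.
2. **Percent change.** Keep the exclusion if wished, but state the number of periods excluded for each antibody, and note that selecting on a baseline of 20 or more with a floor tilts the retained change towards a fall. Alternatively, show the all-periods floored change beside it. That version has no such tilt when nothing changes, but it understates true movements below the floor.
3. **Shift table.** For each antibody, tabulate below 20 versus 20 or more RU/mL from TPnB to the last on-treatment sample, with follow-up samples shown separately. The phases and subperiods in SAP 2.2.1 already allow this split.

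The cost is a revision to SAP 4.2.2 and 4.2.3, recorded in SAP section 6, and one extra table from data already collected. Study conduct does not change. The downside is that the actual-value summaries will contain more floored values, which the footnote covers.

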CRoff	complete remission off OCS therapy
CTCAE	Common Terminology Criteria for Adverse Events
CTP	clinical trial protocol
CWS	cumulative worsening score
DBP	diastolic blood pressure
DLQI	dermatology life quality index
ECG	electrocardiogram
eCRF	electronic case report form
EDV	early discontinuation visit
EFG	efgartigimod
eGFR	estimated glomerular filtration rate
EoTP	end of treatment period

	Statistical Analysis Plan	
ARGX-113-2010	Final analysis	Final 1.0 of 29APR2025

EQ-5D-5L	EuroQoL 5 Dimensions 5 Levels
FU	follow-up
GM	geometric mean
GSD	geometric standard deviation
GTI	glucocorticoid toxicity index
GTI-SL	glucocorticoid toxicity index - specific list
HR	heart rate
ICF	informed consent form
ICH	International Council for Harmonization of Technical Requirements for Pharmaceuticals for Human Use
ID	identification
IGA-BP	investigator global assessment of bullous pemphigoid
█	█
IMP	investigational medicinal product
IRR	injection-related reaction
ISR	injection site reaction
MedDRA	Medical Dictionary for Regulatory Activities
NAb	neutralizing antibody
NA	not applicable
NCI	National Cancer Institute
OCS	oral corticosteroids
OLE	open-label extension
PAS	participant analysis set
PD	pharmacodynamic(s)
PI	principal investigator
PRO	patient-reported outcome
PT	preferred term
PYFU	patient years of follow-up
QoL	quality of life
QTc	corrected QT interval
QTcB	Bazett's corrected QT interval
QTcF	Fridericia's corrected QT interval
rHuPH20	recombinant human hyaluronidase PH20
ROL	rollover analysis set

	Statistical Analysis Plan	
ARGX-113-2010	Final analysis	Final 1.0 of 29APR2025

SAE	serious adverse event
SAF	safety analysis set
SAP	statistical analysis plan
SBP	systolic blood pressure
SC	subcutaneous(ly)
SDTM	study data tabulation model
SGS CR	SGS Clinical Research
SoA	schedule of activities
SoC	standard of care
SOC	system organ class
SOP	standard operating procedure
SMQ	Standardized MedDRA Queries
STAT	statistics
TCS	topical corticosteroids
TEAE	treatment-emergent adverse event
TLF	tables, listings, and figures
VS	vital signs
WHO	World Health Organization
WI	work instruction

	Statistical Analysis Plan	
ARGX-113-2010	Final analysis	Final 1.0 of 29APR2025

DEFINITION OF TERMS

CRF	A printed, optical, or electronic document designed to record protocol required information to be reported to the sponsor for each study participant.

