2.4 PRESENTATION OF RESULTS

2.4.1 Calculation of descriptive statistics and percentages

Descriptive statistics for continuous variables will include the number of nonmissing observations, arithmetic mean, standard deviation (SD), standard error (SE), median, minimum, Q1, Q3 and maximum.

Descriptive statistics for immunogenicity titer values will also include geometric mean (GM) and geometric standard deviation (GSD).

Mean, median, Q1, Q3, GM and GSD will be presented with one more decimal place than the reported values. SE and SD will be presented with two more decimal places than the reported values. Minimum and maximum will be presented with the same number of decimal places as the reported values.

Event-type safety data will be summarized by presenting the number and percentage of participants with an event, and the number of events. The denominator will be all participants in the PAS.

	Statistical Analysis Plan	
ARGX-113-2010	Final analysis	Final 1.0 of 29APR2025

For frequency tabulations and cross-tabulations, the denominator will be the number of participants with nonmissing values in the PAS. For tables where results are shown by analysis visit, the denominator will be the number of participants with nonmissing values in the PAS per analysis visit. For cross-tabulations of postbaseline results versus study baseline results, a ‘missing’ category will be shown for baseline results, if applicable, and included in the calculations of percentages.

Percentages will be presented with one decimal place.

	Statistical Analysis Plan	
ARGX-113-2010	Final analysis	Final 1.0 of 29APR2025

2.4.2 *Presentation of treatments*

The following treatment arm label will be used in displays in the ROL analysis set:

- Total

The following treatment arm label will be used in displays in the SAF analysis set:

- Total Efgartigimod PH20 SC

2.4.3 *Ordering in tables, listings, and figures*

In tables showing several parameters, each parameter will begin on a new page and parameters will be sorted alphabetically, within the parameter category if applicable.

Listings will be ordered by participant identifier and, if applicable, by phase/period/subperiod, analysis visit, and time point, unless specified otherwise.

	Statistical Analysis Plan	
ARGX-113-2010	Final analysis	Final 1.0 of 29APR2025

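### The SAP's GSD of pharmacodynamic percent change is 100{exp(SD) − 1}, which is neither the geometric SD nor a width in percentage points

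*SAP*

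**What the plan says.** SAP 4.2.2 gives one formula for two statistics. It begins "GM and GSD of percent changes from baseline are calculated as" and then states 100{exp(θ) − 1}, where θ is "respectively the arithmetic mean and arithmetic SD of a variable calculated as" log(aval) − log(base). The GM is therefore 100{exp(mean) − 1} and the GSD is 100{exp(SD) − 1}.

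SAP 4.2.3 carries both into the tables: "Descriptive statistics of the actual values and percent changes from TPnB will also include GM and GSD". The list of abbreviations expands GSD only as "geometric standard deviation". No formula is given for the GSD of actual values, nor for the GSD of antibody titers in SAP 2.4.1. Neither 4.2.2 nor 4.2.3 says that the percent-change GSD must be applied multiplicatively.

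The additional secondary endpoint concerned is "Percent change from baseline over time for anti-BP180 and anti-BP230 antibody levels" (SAP 1.1).

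**The concern.** Subtracting 1 makes sense for a location measure: a ratio of 1 means no change, so exp(mean) − 1 is the geometric mean relative change. A geometric SD is a spread factor by which the ratio is multiplied or divided. Taking 1 from it and multiplying by 100 gives a figure in percent that does not match its label.

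The layout makes a misreading easy. The percent-change rows also carry an arithmetic SD, which is in percentage points (SAP 2.4.1). A GSD also given in percent invites the same plus-or-minus use. If the GSD of actual values is computed in the usual way as exp(SD), which is an assumption because the SAP gives no formula, one label covers two scales in the same table. At stake is how readers judge the consistency of the antibody reduction between participants.

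**Working it through.** **Inputs.** From SAP 4.2.2: the transform 100{exp(θ) − 1}, with θ equal to the mean m or the SD s of log(aval) − log(base). The logarithm is taken as natural because it is paired with exp. The documents state no GM, GSD or log-scale SD, so there is no planned figure to reproduce. All values of GM and s below are assumptions.

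**Formulas.** Write g = exp(m) and k = exp(s).

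- SAP: GM% = 100(g − 1); GSD% = 100(k − 1).
- Geometric SD: k.
- Multiplicative 1-SD range: 100(g/k − 1) to 100(gk − 1).
- Range if a reader adds and subtracts: GM% ± GSD%, that is 100(g − k) to 100(g + k − 2).

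**One case in full: GM −60%, s = 0.5.** Here g = 0.40 and k = exp(0.5) = 1.649. The SAP figure is 100 × 0.649 = 64.9. Adding and subtracting gives −60 − 64.9 = −124.9 and −60 + 64.9 = +4.9. The multiplicative range is 0.40/1.649 = 0.243, or −75.7%, to 0.40 × 1.649 = 0.659, or −34.1%.

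**Other assumed cases.**

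| GM | s | SAP GSD (%) | exp(s) | Added and subtracted | Multiplicative 1-SD range |
|---|---|---|---|---|---|
| −60% | 0.3 | 35.0 | 1.350 | −95.0% to −25.0% | −70.4% to −46.0% |
| −60% | 0.5 | 64.9 | 1.649 | −124.9% to +4.9% | −75.7% to −34.1% |
| −60% | 0.7 | 101.4 | 2.014 | −161.4% to +41.4% | −80.1% to −19.4% |
| −50% | 0.7 | 101.4 | 2.014 | −151.4% to +51.4% | −75.2% to +0.7% |
| −30% | 0.5 | 64.9 | 1.649 | −94.9% to +34.9% | −57.5% to +15.4% |
| 0% | 0.5 | 64.9 | 1.649 | −64.9% to +64.9% | −39.3% to +64.9% |

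**Direction of the error.** As proportions, the additive lower limit lies (k − 1)(1 − g/k) below the multiplicative one, and the additive upper limit lies (k − 1)(1 − g) above it. Both are positive when g < 1 and s > 0, so with an average fall the range is too wide at both ends. At GM 0% the upper limits coincide, as the last row shows.

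**When −100% is passed.** 100(g − k) < −100 if and only if k > 1 + g, that is s > ln(1 + g). The threshold for s is 0.693 at GM 0%, 0.531 at −30%, 0.405 at −50%, 0.336 at −60% and 0.182 at −80%. The multiplicative lower limit is always above −100%.

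**Recoverability.** exp(s) = 1 + GSD%/100; for example 1 + 64.9/100 = 1.649.

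**The case against.** The strongest reply is that the figure is an unconventional percent form of the geometric SD. The formula is stated openly, exp(SD) can be recovered exactly, and no information is lost. The SAP plans no GM ± GSD interval; it lists the two as separate statistics: "Mean, median, Q1, Q3, GM and GSD will be presented with one more decimal place than the reported values". SAP 2.4.1 also calls for the SD, SE, median, quartiles, minimum and maximum of continuous variables. The quartiles and extremes of percent change cannot fall below −100% for non-negative antibody levels. The table template is in a sponsor library outside these documents, so a clarifying footnote there cannot be ruled out.

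All of this stands, and it limits the point. A reader might infer that the plan itself implies falls of more than 100%, or that the whole pharmacodynamic display of spread is wrong. The documents do not support either reading. The first needs a subtraction that the SAP never specifies and also exp(SD) > 1 + exp(mean), and no log SD is given from which to judge whether that would occur. The second overlooks the other dispersion statistics in the same tables. Nor is the distortion confined to the downward side: under the additive reading with an average fall, both limits are too wide.

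The reply does not rescue the label. Someone who has only the table can recover the geometric SD only by knowing the formula in SAP 4.2.2.

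**Conclusion.** The point holds as a minor error of formula and label. Under the heading GSD, the stated rule yields 100{exp(SD) − 1}; with an assumed log SD of 0.5 that is 64.9, where the geometric SD is 1.649. The figure cannot be used as a plus-or-minus width. If it is so used when levels fall on average, the range is too wide on both sides: by about 49 percentage points below and 39 above at an assumed GM of −60% and log SD of 0.5. Whether the range also passes −100% depends on the data: at GM −60% it does so with log SD 0.5 but not with 0.3.

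The consequence is confined to descriptive pharmacodynamic tables at the last assessment of a treatment period. SAP 1.3 states "No formal hypothesis testing will be conducted in this open-label study", and the GM, the primary endpoints and the efficacy endpoints do not change. The sizes rest on the assumed GM and log SD values and on a natural logarithm.

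**What to change.** In SAP 4.2.2 and the table shell, keep 100{exp(mean) − 1} for the GM of percent change. For spread, report either the ratio exp(SD), labelled as a multiplicative factor, or the range 100{exp(mean − SD) − 1} to 100{exp(mean + SD) − 1}. State the formula for the GSD of actual values too, so that the label has one meaning throughout the table.

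A back-transformed 95% CI for the GM, 100{exp(mean ± t × SE) − 1}, may be added. It shows the precision of the mean and does not replace the measure of spread.

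The cost is one formula, a row label and an entry in the SAP's version history. No new data or analysis is needed.
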